9. STUDY CALENDAR

This study calendar is for patients enrolled in the interventional arm who will receive radiation therapy on study. For patients in the separate registry arm, clinic visits,

laboratory draws, and scans will be per standard of care and are not mandated to be on a specific schedule. For interventional arm patients, after disease progression or unacceptable toxicity, the patient enters the long-term follow-up period and visit/imaging schedule will be at the discretion of the treating medical oncologist and not mandated by the study.

All treatment and evaluation items in the study calendar are part of standard medical care, except for the peripheral blood biomarker lab draw which is a research procedure. Also, if a patient has pre-radiation CT-guided biopsy or fiducial placement for routine clinical purposes, research cores may be obtained during that procedure.

Action	Pre Entry ¹	Pre-RT	Day 1 of RT	Last day of RT	8 weeks after sim ²	16 weeks after sim ²	24 weeks after sim ²	36 weeks after sim ³	48 weeks after sim ³	Every 12 weeks until disease progression or unacceptable toxicity ³	After disease progression or unacceptable toxicity
History & Physical Exam	X				X	X	X	X	X	X ¹¹	
ECOG PS	X				X	X	X	X	X	X ¹¹	
Labs											
CBC/diff.	X ⁹										
CMP	X ⁹										
CT Thorax (Chest), or PET/CT	X				X	X	X	X	X	X ¹¹	
Brain MRI or CT, if known brain metastases	X				X	X	X	X	X	X ¹¹	
Vital status evaluation					X	X	X	X	X	X	X ¹⁰
Study consent		X ¹²									
Toxicity evaluation		X			X	X	X	X	X	X ¹¹	
Fiducial placement (as clinically indicated)		X									
Research cores during fiducial placement (optional)		X									
Radiation therapy			X	X							
Lesion measurements				X ⁴	X ⁵	X ⁵	X ⁵	X ⁵	X ⁵	X ⁵	

Peripheral blood biomarkers (if consented for this portion of study)			X ⁶	X ⁷	X ⁸						
--	--	--	----------------	----------------	----------------	----------------	----------------	----------------	----------------	----------------	--

Sim=simulation

¹ Within 4 weeks prior to enrollment

² +/- 2 weeks

³ +/- 4 weeks

⁴ After the last day of RT or up to 4 weeks following the completion of RT: For each radiation treated lesion, document diameter on sim CT, location and radiation dose.

⁵ Document size of each radiation treated lesion. Also document RECIST response compared to radiation SIM CT. For follow-up time points starting with 108 weeks: if imaging studies were not performed, lesion measurements are not required.

⁶ Blood drawn before first fraction of RT or any time up to 14 days before first fraction.

⁷ Blood drawn after last fraction of RT or any time up to 14 days after last fraction.

⁸ Optional

⁹ Labs collected prior to study and prior to each cycle of immunotherapy at the discretion of the treating medical oncologist.

¹⁰ After disease progression/unacceptable toxicity, vital status will be recorded every 6-12 months by chart review and/or telephone calls.

¹¹ Adverse events will be recorded until the 96-week follow-up visit. Starting with the 108-week follow-up visit, adverse events will not be recorded, and the history & physical exam, ECOG PS, and imaging studies will all be optional.

¹² Within 60 days prior to first dose of study radiation therapy

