3.1 Inclusion Criteria

1. Has stage IV non-small cell lung cancer, or initially stage I-III disease with distant metastatic recurrence
2. Age ≥ 18
3. Has been receiving anti-PD-1 or anti-PD-L1 immunotherapy for at least four weeks (refer to section 4.2.1)
4. Has had restaging imaging after initiation of immunotherapy, at least 4 weeks after pre-immunotherapy baseline imaging. CT or PET/CT of at least chest/upper abdomen must be performed within 4 weeks prior to registration. For patients with history of brain metastases, brain MRI or CT is required within 4 weeks of registration; for other patients brain MRI or CT is required within 12 weeks of registration. Diagnostic PET/CT performed as part of radiation simulation can be used as the restaging imaging.
5. Most recent imaging shows measurable disease as defined by RECIST 1.1
6. Evaluation by a Stanford medical oncologist must show:
 - a. The patient is expected to continue on immunotherapy for at least three more months
 - b. Imaging must show response, stable disease, or modest progression
 - c. If there is modest progression, the patient must be clinically stable in terms of performance status and overall disease-related symptoms
7. Has at least one extracranial tumor safely treatable with radical-dose radiation therapy and that has not been previously treated with radiation
8. ECOG performance status 0-2
9. Has the ability to understand and the willingness to sign a written informed consent document.

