10.1.4 Measurement Time Points

Patients on the interventional arm will undergo CT scans to cover all known sites of disease at 8 week intervals (± 2 weeks) for the first 24 weeks, and then at 12 week intervals (± 4 weeks). PET-CT is an acceptable alternative. Patients with known brain metastases will have brain MRI or CT at 3-4 month intervals (up to 6 month intervals acceptable if last treatment for brain metastases is 1 year or more prior to the scan). After disease progression or unacceptable toxicity, imaging schedule will be at the discretion of the treating medical oncologist.

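### The study calendar and section 10.1.4 contradict each other on the body and brain imaging that decides PFS24, leaving room for undetected progression by week 24

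*Protocol*

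**What the plan says.** **Body imaging.** The calendar in protocol section 9 lists "CT Thorax (Chest), or PET/CT" before entry and at 8, 16, 24, 36 and 48 weeks after simulation. No footnote widens the CT beyond the chest. Section 10.1.4 says "Patients on the interventional arm will undergo CT scans to cover all known sites of disease at 8 week intervals" up to week 24, and adds that "PET-CT is an acceptable alternative".

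**Brain imaging.** The calendar row "Brain MRI or CT, if known brain metastases" is marked at the same visits, including weeks 8, 16 and 24. Section 10.1.4 says "Patients with known brain metastases will have brain MRI or CT at 3-4 month intervals", with "up to 6 month intervals acceptable if last treatment for brain metastases is 1 year or more prior to the scan".

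**What the scans feed.** Section 10.1.2 defines PFS24 as the proportion alive without RECIST 1.1 progression 24 weeks after study entry, with no restriction by site. Section 10.1.3 judges progression from CT, PET/CT, brain MRI and clinic visits, with the simulation CT as the preferred baseline. Section 4.3.3 wants that CT generally to take in all known extracranial disease. Calendar footnote 5 asks for RECIST response against it at each follow-up visit.

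**The concern.** PFS24 is a yes/no status in stage IV disease. A patient is a success unless progression or death is recorded, so the endpoint depends on which sites were imaged and when. Two passages of the same protocol give different answers. A team working from the calendar may order a chest CT for a patient with known liver or adrenal disease. A team working from 10.1.4 may leave the brain unscanned for months.

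The resulting error runs one way: a progression that is not seen turns a failure into a success. The result is tested against a fixed 35%, and section 12.2.1 plans no formal comparison with the registry arm, so no concurrent group is in place to show the same loss.

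**Working it through.** **Step 1. Passages side by side, to week 24.**

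| | Calendar, section 9 | Section 10.1.4 | Weaker text |
|---|---|---|---|
| Body | Chest CT, or PET/CT | CT of all known sites, or PET-CT | Calendar |
| Brain, if metastases known | Weeks 8, 16, 24 | Every 3-4 months; up to 6 months if last brain treatment was at least 1 year before the scan | 10.1.4 |

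For a patient with known disease outside the chest, a chest CT meets the calendar row but not 10.1.4. It also cannot supply the RECIST response that footnote 5 requires against a baseline covering the extrathoracic lesions, so the calendar is at odds with its own footnote.

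**Step 2. Brain intervals in weeks** (30.44 days per month).
- 3 months: 3 × 30.44 / 7 = 13.0 weeks. 4 months: 4 × 30.44 / 7 = 17.4 weeks. The usual interval therefore gives at least one brain scan before week 24.
- 6 months: 6 × 30.44 / 7 = 26.1 weeks, longer than the endpoint window. Inclusion criterion 4 requires brain imaging within 4 weeks of registration when there is a history of brain metastases. Counted from that scan, the next one falls about 22 to 26 weeks after registration. Some patients in this subgroup may have no brain scan between entry and week 24.

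**Step 3. The plan's own figure.** Section 12.3 gives null 35%, alternative 52%, one-sided alpha 0.1, power at least 80%, exact binomial test, 39 evaluable patients. The smallest r with P(X ≥ r | 39, 0.35) ≤ 0.10 is r = 18:
- P(X ≥ 18 | 39, 0.35) = 0.0996
- P(X ≥ 18 | 39, 0.52) = 0.8135

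The 39 reproduces. Almost all of the 0.10 is used. If all 43 enrolled patients are analysed, the cut-off is 20, with exact alpha 0.0792 and power 0.8087.

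**Step 4. Illustration of missed progression.** Let m be the share of all week-24 failures that go undetected. The documents give no value, so m is an assumption. At a true PFS24 of 35%,

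observed PFS24 = 0.35 + 0.65 × m.

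| m | Observed PFS24 | Patients misclassified of 39 (39 × 0.65 × m) | Type I error, n=39, 18 or more | Type I error, n=43, 20 or more |
|---|---|---|---|---|
| 0 | 35.0% | 0 | 10.0% | 7.9% |
| 1% | 35.7% | 0.25 | 11.6% | 9.4% |
| 2% | 36.3% | 0.51 | 13.3% | 11.0% |
| 5% | 38.3% | 1.27 | 19.7% | 16.9% |
| 10% | 41.5% | 2.54 | 33.2% | 30.2% |

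The denominator of m includes deaths, which imaging cannot miss. Only symptom-free progression confined to an unscanned site contributes to the numerator.

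**The case against.** The strongest reply is that the conflicts are narrower than they look, and most of it stands.

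- A reader might infer that the calendar asks for chest CT alone. It does not: PET/CT is in the same row. Chest CT is the least that satisfies it.
- A reader might infer that a team could do the least in each case and still comply. The documents do not support that. Section 10.1.4 is mandatory, so a chest CT in a patient with known extrathoracic disease breaches it; the longer brain interval departs from the calendar. The conflicts run in opposite directions, and neither passage alone leaves both gaps open.
- Footnote 5 already points towards full body coverage, since the RECIST comparison cannot otherwise be completed.
- Inclusion criterion 4, "CT or PET/CT of at least chest/upper abdomen must be performed within 4 weeks prior to registration", might be read as a third definition of follow-up coverage. It is only a minimum for the eligibility scan.
- The long brain interval applies only where the last brain treatment was at least a year before the scan, and the next scan may fall close to the week-24 visit. Patients without known brain metastases are not touched by the brain conflict.
- Clinic visits count towards progression and deaths are failures, so symptomatic and fatal events are still captured.
- A reader might infer that nothing offsets the bias in the comparison with history. The documents do not say how the historical trials imaged brain or extrathoracic sites, so the net effect against the 35% is unknown.

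What remains is that the protocol fixes the scan schedule twice, differently, for its primary endpoint. A statistical analysis plan could not settle afterwards which scans should have been done.

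**Conclusion.** The point holds as a contradiction in the current text that bears on the primary endpoint. If the weaker passage is followed, some progression can go unseen, and unseen progression can only raise the observed PFS24.

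It does not follow that PFS24 is overstated, or that the false-positive rate is doubled or tripled. Those sizes appear only at assumed miss rates of 5% and 10% of all failures. At 1% or 2% the type I error at n=39 moves from 10.0% to 11.6% or 13.3%. The documents support no particular rate. The range shows that the design has little slack: about 1.3 misclassified patients of 39 corresponds to the 5% row. The sample-size figures themselves are not in error.

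**What to change.** 1. Reconcile the calendar's body-imaging row with section 10.1.4 so that both state the same coverage, sufficient to assess RECIST 1.1 at all known disease sites.
2. Reconcile the brain-imaging row with 10.1.4 so that both give the same times through week 24.
3. Report how many patients recorded as progression-free lacked imaging of all known sites (including brain where metastases are known) in the week-24 window, and give a sensitivity PFS24 that counts them as failures. If the statistical analysis plan, not seen here, already provides this, nothing need be added.

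The cost is mainly wording in two places and one extra tabulation. Section 9 already describes the calendar's imaging as standard care. The sensitivity PFS24 may come out slightly lower than the primary figure.

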10. MEASUREMENTS

10.1 Primary Outcome

Title: Progression-free survival at 24 weeks (PFS24)

Time frame: 24 weeks after study entry

Safety issue: no

10.1.1 Relevant Subset

Patients who enroll on the interventional arm and receive radiation therapy on protocol will be analyzed.

Patients who meet eligibility criteria but choose not to enroll on protocol treatment will be offered the option of participating in a registry arm. These patients will receive standard of care treatment and follow-up (including imaging), not dictated by the protocol. They will be followed for endpoints including radiographic progression, discontinuation of immunotherapy, and death.

10.1.2 Measurement Definition

Progression-free survival at 24 weeks (PFS24) is proportion of patients without RECIST 1.1 disease progression or death 24 weeks from date of study entry.

10.1.3 Measurement Methods

The baseline imaging study on the interventional arm will be the radiation simulation CT when possible. If not all known lesions are visible on the simulation CT, the most recent prior diagnostic CT or PET/CT can be used instead. Progression will be evaluated by follow up CT, PET/CT, and brain MRI imaging and clinic visits. Progression compared to simulation CT will be defined as per the RECIST 1.1 criteria.

10.1.4 Measurement Time Points

Patients on the interventional arm will undergo CT scans to cover all known sites of disease at 8 week intervals (± 2 weeks) for the first 24 weeks, and then at 12 week intervals (± 4 weeks). PET-CT is an acceptable alternative. Patients with known brain metastases will have brain MRI or CT at 3-4 month intervals (up to 6 month intervals acceptable if last treatment for brain metastases is 1 year or more prior to the scan). After disease progression or unacceptable toxicity, imaging schedule will be at the discretion of the treating medical oncologist.

10.1.5 Response Review

There are no plans for response review by an independent third party.

10.2 Secondary outcome #1

Title: Acute (0-6 months) and late (>6 months) grade 3-5 toxicity

Time frame: 0-4 years after study entry

Safety issue: yes

10.2.1 Relevant Subset

Patients who enroll on the interventional arm and receive radiation therapy on protocol will be analyzed.

10.2.2 Measurement Definition

Acute toxicity is defined as toxicity that occurs 0-6 months after first day of radiation therapy. Late toxicity is toxicity that occurs >6 months after first day of radiation therapy. Toxicity is measured with CTCAE v4.

10.2.3 Measurement Methods

Toxicity will be assessed at follow-up clinic visits. Also, patients will be followed for hospitalization and other medical events.

10.2.4 Measurement Time Points

Follow-up clinic visits at 8 week intervals (± 2 weeks) for the first 24 weeks, and then at 12 week intervals (± 4 weeks) until disease progression.

If there is RECIST 1.1 disease progression or unacceptable toxicity, the patient will be considered to be off of protocol therapy and will not be required to be seen at protocol specified follow up time points. The patient will then be followed for survival outcomes collected during standard of care visits, with study data collection typically occurring every 6-12 months. If the patient is lost to follow-up and not seen at Stanford, phone calls will be performed to check for survival status annually.

10.2.5 Response Review

There are no plans for response review by an independent third party.

10.3 Secondary outcome #2

Title: Overall survival

Time frame: 0-4 years after study entry

Safety issue: no

10.3.1 Relevant Subset

Patients who enroll on the interventional arm and receive radiation therapy on protocol will be included in this analysis. Patients who enroll on the registry arm will also be analyzed as a separate arm.

10.3.2 Measurement

Definition Time from study

entry to death.

10.3.3 Measurement Methods

The electronic medical record will be monitored for patient deaths.

10.3.4 Measurement Time Points

There is no specific time point for this measurement.

10.3.5 Response Review

There are no plans for response review by an independent third party.

10.4 Secondary outcome #3

Title: Correlation of circulating tumor DNA (ratio of post-RT to pre-RT level) with

radiographic response

Time frame: 0 to approximately 1 year after study entry

Safety issue: no

10.4.1 Relevant Subset

Patients who enroll on the interventional arm, receive radiation therapy on protocol, and have pre- and post-RT research blood draws will be included in this analysis.

10.4.2 Measurement Definition

- ctDNA measured as percentage of total circulating free DNA
- Radiographic tumor assessments using RECIST 1.1 criteria, using radiation simulation CT as baseline scan. Best response after RT will be recorded.

10.4.3 Measurement Methods

ctDNA levels will be measured using CAncer Personalized Profiling by deep Sequencing (CAPP-Seq).

10.4.4 Measurement Time Points

- ctDNA specimens (also see section 8.1.1): The first specimen will be drawn on the first day of RT (before RT), or up to 14 days earlier. The second specimen will be drawn on the last day of RT (after RT), or up to 14 days later.
- Radiographic response: Each post-RT restaging imaging study will be scored for RECIST 1.1 response, until best response is achieved.

10.4.5 Response Review

There are no plans for response review by an independent third party.

10.5 Secondary outcome #4

Title: Correlation of immune markers in peripheral blood with radiographic response

Time frame: 0 to approximately 1 year after study entry

Safety issue: no

10.5.1 Relevant Subset

Patients who enroll on the interventional arm, receive radiation therapy on protocol, and have pre- and post-RT research blood draws will be included in this analysis.

10.5.2 Measurement Definition

- Immune markers including frequency of myeloid-derived suppressor cells and antigen- specific CD8+ T cells
- Radiographic tumor assessments using RECIST 1.1 criteria, using radiation simulation CT as baseline scan. Best response after RT will be recorded.

Measurement Methods

Immune markers will be measured using flow cytometry performed by the Human Immune Monitoring Core at Stanford.

10.5.3 Measurement Time Points

- Peripheral blood flow cytometry specimens (also see section 8.1.1): The first specimen will be drawn on the first day of RT (before RT), or up to 14 days earlier. The second specimen will be drawn on the last day of RT (after RT), or up to 14 days after.
- Radiographic response: Each post-RT restaging imaging study will be scored for RECIST 1.1 response, until best response is achieved.

10.5.4 Response Review

There are no plans for response review by an independent third party.

10.6 Secondary outcome #5

Title: Dose-limiting toxicity (DLT)

Time frame: 0-4 years after study entry

Safety issue: yes

10.6.1 Relevant Subset

Patients who enroll on the interventional arm and receive at least one dose of radiation therapy on protocol will be analyzed.

10.6.2 Measurement Definition

Any grade 3-5 toxicity related to study radiation therapy, except the following:

- grade 4 radiation dermatitis or mucositis that reduces to grade 2 or lower within 1 month after completion of study radiation therapy
- grade 3 radiation dermatitis, mucositis, pain, dysphagia, diarrhea, fatigue, anorexia, weight loss, esophagitis, endocrine disorder

10.6.3 Measurement Methods

Toxicity will be assessed at follow-up clinic visits. Also, patients will be followed for hospitalization and other medical events.

10.6.4 Measurement Time Points

Follow-up clinic visits at 8 week intervals (± 2 weeks) for the first 24 weeks, and then at 12 week intervals (± 4 weeks) until disease progression or unacceptable toxicity.

10.6.5 Response Review

There are no plans for response review by an independent third party.

11. REGULATORY CONSIDERATIONS

11.1 Institutional Review of Protocol

The protocol, the proposed informed consent and all forms of participant information related to the study (e.g. advertisements used to recruit participants) will be reviewed and approved by the Stanford IRB and Stanford Cancer Institute Scientific Review Committee (SRC). Any changes made to the protocol will be submitted as a modification and will be approved by the IRB prior to implementation. The Protocol Director will disseminate the protocol amendment information to all participating investigators.

11.2 Data and Safety Monitoring Plan

The Stanford Cancer Institute Data and Safety Monitoring Committee (DSMC) will be the monitoring entity for this study. The DSMC will audit study-related activities to determine whether the study has been conducted in accordance with the protocol, local standard operating procedures, FDA regulations, and Good Clinical Practice (GCP).

This may include review of the following types of documents participating in the study: regulatory binders, case report forms, eligibility checklists, and source documents. In addition, the DSMC will regularly review serious adverse events and protocol deviations associated with the research to ensure the protection of human subjects. Results of the DSMC audit will be communicated to the IRB and the appropriate regulatory authorities at the time of continuing review, or in an expedited fashion, as needed.

While study accrual is ongoing, the study team will provide the DSMC with a yearly report that lists a summary of the frequency and severity of grade 3-5 adverse events observed so far.

The DSMC will also review results of the single interim safety analysis (see section 12.2), and based on this review will provide a determination of whether patient accrual should continue.

11.3 Data Management Plan

The Protocol Director, or his/her designee, will prepare and maintain adequate and accurate participant case histories with observations and data pertinent to the study. Study specific Case Report Forms (CRFs) will document treatment outcomes for data analysis. Case report forms will be developed using REDCap database system and will be maintained by the Clinical Research Coordinator assigned to this study.

The study team will hold monthly meetings. Topics for discussion will include screening of candidates, eligibility, accrual progress, data entry completeness, adverse event grading and attribution, and serious adverse events.

12. STATISTICAL CONSIDERATIONS

12.1 Primary and Secondary Endpoints

Primary endpoint

Determine if progression-free survival at 24 weeks (PFS24, measured from study entry) with this treatment combination is improved compared to historical controls who received immunotherapy without radiation therapy

Secondary endpoints

- Acute (0-6 months) and late (>6 months) grade 3-5 toxicity (CTCAE v4)
- Overall survival
- Correlation of circulating tumor DNA (ratio of post-RT to pre-RT level) with radiographic response
- Correlation of immune markers in peripheral blood with radiographic response
- Dose-limiting toxicity

Exploratory endpoints

- Progression-free survival with immune-related response criteria
- Time to discontinuation of study immunotherapy agent
- Patterns of response and progression, including abscopal responses

